#### **9.4.5.3. Vital Signs**

Systolic and diastolic blood pressure, pulse rate, respiratory rate, body temperature, and oxygen saturation will be listed for each participant. If applicable, summary statistics (mean change, percentage change from Baseline, and absolute change from Baseline) by treatment group (dose levels of brensocatic and pooled placebo) and by treatment group within each stratum (CFTR modulator and non-modulator) at each timepoint and EOT will be provided. Baseline values are

defined as vital signs collected prior to the first dose on Day 1. The AEs reported in association with the clinically significant abnormalities in vital signs will be presented in the relevant AE listings.

#### **9.4.5.4. Physical Examination**

Physical examination postbaseline findings that meet the criteria for an AE will be listed in the relevant AE listings.

#### **9.4.5.5. Electrocardiogram**

The results of the 12-lead ECG tracings will be listed for each participant. Postbaseline ECG results that meet the criteria for an AE will be listed in the relevant AE listings. If applicable, summary statistics of ECG results will be provided.

### **9.5. Interim Analysis**

No formal interim analysis is planned for this study.

## **10. SUPPORTING DOCUMENTATION AND OPERATIONAL CONSIDERATIONS**

### **10.1. Appendix 1: Regulatory, Ethical, and Study Oversight Considerations**

#### **10.1.1. Regulatory and Ethical Considerations**

This study will be conducted in accordance with the protocol and with the following:

- Consensus ethical principles derived from international guidelines including the Declaration of Helsinki and Council for International Organizations of Medical Sciences (CIOMS) International Ethical Guidelines
- Applicable ICH Good Clinical Practice (GCP) Guidelines
- Applicable laws and regulations

The protocol, protocol amendments, ICF, Investigator's Brochure, and other relevant documents must be submitted to an IRB by the Investigator and reviewed and approved by the IRB before the study is initiated.

Any amendments to the protocol will require IRB approval before implementation of changes made to the study design, except for changes necessary to eliminate an immediate hazard to study participants.

Protocols and any substantial amendments to the protocol will require health authority approval prior to initiation except for changes necessary to eliminate an immediate hazard to study participants.

The Investigator will be responsible for the following:

- Providing written summaries of the status of the study to the IRB annually or more frequently in accordance with the requirements, policies, and procedures established by the IRB
- Notifying the IRB of SAEs or other significant safety findings as required by IRB procedures
- Providing oversight of the conduct of the study at the site and adherence to requirements of 21 CFR, ICH guidelines, the IRB, and all other applicable local regulations

#### **10.1.2. Protocol Deviations**

The Investigator must conduct the study in compliance with the protocol as agreed to by Insmmed and, if required, by the regulatory authority(ies), and which was given approval/favorable opinion by the IRB.

The Investigator must notify the IRB of deviations from the protocol in accordance with IRB reporting requirements.

As of May 2020, due to concern regarding COVID-19, there may be restrictions to participant attendance at in-clinic visits or elective inpatient admissions. In the event participants are restricted to attend in-clinic visits, or if the participant has concern regarding travel and attending in-clinic visits (due to potential public health concerns), the site must contact Insmmed on how to conduct the scheduled assessments, and decisions must be documented in the source documentation. Where necessary, in-clinic visits may be conducted via telemedicine link and home health care visits.

### **10.1.3. Public Health Emergency Situations**

During the COVID-19 public health emergency, Insmmed, IRBs, and Investigators shall follow the most current version of local guidance to assure the safety of study participants, maintain compliance with GCP, and minimize risks to study integrity. The continuity of clinical study conduct and oversight may require implementation of temporary or alternative mechanisms, which will remain in effect only for the duration of the local public health emergency. Examples of such mechanisms may include, but are not limited to, any of the following: telephone contact, virtual visits, telemedicine visits, online meetings, non-invasive remote monitoring devices, use of local clinic or laboratory locations, and home visits by skilled staff. The site must contact Insmmed on how and when to implement temporary and/or alternative mechanism of scheduled assessments, and all decisions taken must be documented in the source documentation. Additionally, all temporary mechanisms utilized, and the resulting deviations from planned study procedures are to be documented as being related to COVID-19.

In a situation where local health authorities declare a public health emergency while the study is ongoing, the suggested guidance in the following subsections must be followed.

#### **10.1.3.1. Continuation or Suspension of the Study**

Ensuring the safety of trial participants is paramount. Insmmed, in consultation with the clinical investigators and IRB, will determine whether the protection of a participant's safety, welfare, and rights are best served by continuing or stopping the trial at the specific site. Such decision will depend on specific circumstances, including the ability to conduct appropriate safety monitoring, the potential impact on the investigational product supply chain, and other considerations.

If the decision is to continue the study, the following considerations will be taken into account:

##### **10.1.3.1.1. Study Recruitment**

The Insmmed will communicate to the sites the decision on whether to continue or suspend recruitment after considering the specific circumstances of each site, recommendation by the IRB, and its local health authority mandates. If, due to COVID-19, study discontinuation exceeds the assumed rate, Insmmed may allow enrollment past the assumed sample size.

##### **10.1.3.1.2. Participants Already Enrolled in the Study**

If the decision is to continue the participation of participants already enrolled, the following steps must be taken:

- If a participant is not able to complete a protocol specified study visit, it may be necessary to adjust the visit schedule, convert in-clinic visits to telemedicine visits, and/or postpone study procedures until the next available in-clinic study visit. If there is information available from previous visits (ie, laboratory assessments) that requires follow-up procedures or other safety assessments, the Investigator will decide if an on-site visit or home healthcare visit is required or whether the participant's safety can be preserved by other means.

#### **10.1.3.1.3. Participants Infected by COVID-19**

If a participant has had a past documented mild to moderate COVID-19 infection prior to enrollment in the trial but the participant has recovered and the current diagnostic tests are negative (negative antigen by any diagnostic laboratory kit), the participant can be screened, at the Investigator's discretion. Participants who experienced hospitalization, severe disease, and/or COVID-19 ARDS must be excluded.

If a participant has a documented infection by COVID-19 while in the trial, the event will be reported as an AE or SAE, depending on the criteria. The Investigator will follow the guidance provided by health authorities in the treatment of those participants.

#### **10.1.4. Financial Disclosure**

The disclosed financial interest of the Investigator must be collected before Screening of the first participant, following study completion at the Investigator site and 1 year following overall study completion. The Investigator must promptly update this information if any relevant changes occur during this period.

#### **10.1.5. Informed Consent Process**

Before a participant's participation in the study, it is the Investigator's responsibility to obtain freely given consent, in writing, from the participant or legally acceptable representative after adequate explanation of the aims, methods, anticipated benefits, and potential hazards of the study and before any protocol-specific screening procedures or any study IMPs are administered. A legally acceptable representative is an individual or other body authorized under applicable law to consent, on behalf of a prospective participant, to the participant's participation in the clinical study. An informed consent document that includes both information about the study and the consent form will be prepared and given to the participant. This document will contain all the elements required by the ICH E6 (R2) Guideline for GCP and any additional elements required by local regulations. The written ICF must be prepared in the local language(s) of the potential participant population.

In obtaining and documenting informed consent, the Investigator must comply with the applicable regulatory requirements and must adhere to GCP and to the ethical principles that have their origin in the Declaration of Helsinki. The consent form and any revision(s) must be approved by the IRB prior to being provided to potential participants.

The participant's written informed consent (written or electronic) must be obtained prior to his/her participation in the study, and must be documented in the participant's medical records, as required by applicable regulations. The ICF must be signed and personally dated by the

participant or a legally acceptable representative and by the person who conducted the informed consent discussion (not necessarily the Investigator). The signed ICF must be retained in accordance with institutional policy, and a copy of the signed consent form must be provided to the participant or legal representative. The date and time that informed consent was given must be recorded in the CRF.

Participants who are rescreened are required to sign a new ICF.

Informed consent must be obtained prior to participation in the study, including procedures to be performed during Screening. For example, after the participant has provided the informed consent, they will be instructed to report bronchodilator use upon returning to the clinic for the Screening spirometry assessment.

#### **10.1.6. Protection of Participant Identification and Confidentiality**

The Investigators and Insmmed will preserve the confidentiality of all participants taking part in the study, in accordance with GCP and local regulations.

The Investigator must ensure that the participant's anonymity is maintained. On the CRF or other documents submitted to Insmmed, participants must be identified by a unique participant identifier as designated by Insmmed. Documents that are not for submission to Insmmed (eg, signed ICFs) must be kept in strict confidence by the Investigator.

In compliance with ICH GCP Guidelines, it is required that the Investigator and institution permit authorized representatives of the company, of the regulatory agency(s), and the IRB direct access to review the participant's original medical records for verification of study-related procedures and data. The Investigator is obligated to inform the participant that his/her study-related records will be reviewed by the above-named representatives without violating the confidentiality of the participant.

Participant names will not be supplied to Insmmed. A participant number will be recorded in the CRF, and if the participant name appears on any other document (eg, laboratory report), it must be obliterated on the copy of the document to be supplied to Insmmed. All records will be kept confidential to the extent provided by federal, state, and local laws. The participants will be informed that representatives of Insmmed, IRB, or regulatory authorities may inspect their medical records to verify the information collected, and that all personal information made available for inspection will be handled in strictest confidence and in accordance with local data protection laws.

The Investigator will maintain a personal participant identification list (participant numbers with the corresponding participant names) to enable records to be identified.

#### **10.1.7. Data Protection**

Participants will be assigned a unique identifier by the Sponsor. Any participant records or datasets that are transferred to the Sponsor will contain the identifier only; participant names or any information that would make the participant identifiable will not be transferred.

The participant must be informed that his/her personal study-related data will be used by the Sponsor in accordance with local data protection law. The level of disclosure must also be

explained to the participant who will be required to give consent for their data to be used as described in the informed consent

The participant must be informed that his/her medical records may be examined by Clinical Quality Assurance auditors or other authorized personnel appointed by the Sponsor, by appropriate IRB members, and by inspectors from regulatory authorities.

#### **10.1.8. Committees Structure**

An SRC will be chartered, comprising:

- Insmmed Vice President of Pipeline Programs
- Insmmed Medical Monitor for Brensocatic Clinical Development Program
- Insmmed Clinical Pharmacology Expert
- Vice President, Drug Safety and Pharmacovigilance (or designee)
- Principal Investigator for the study
- And possible external expert consultants

Participant safety will be continuously monitored by the Sponsor, which includes safety signal detection at any time during the study. After the first 3 cohorts (brensocatic 10, 25, and 40 mg QD) have completed the study, the SRC will review available data (PK and safety data [vital signs, clinical laboratory test values, ECGs, and AEs]) from all cohorts to determine if brensocatic has shown an acceptable safety and PK profile, and whether the brensocatic dose should be escalated to 65 mg QD as planned.

In particular, the SRC will review the following events:

- Any deaths, regardless of causality
- AESIs, including hyperkeratosis, periodontal/gingival events, and infection

Complete details can be found in the SRC charter.

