#### **4.1.5. Safety Review Committee**

Safety monitoring of the study will be conducted by an SRC. After the first 3 cohorts (brensocatib 10, 25, and 40 mg QD) have completed the study, the SRC will review available data (PK and safety data [vital signs, clinical laboratory test values, ECGs, and AEs]) in an unblinded manner from all cohorts to determine if brensocatib has shown an acceptable safety and PK profile and whether the brensocatib dose should be escalated to 65 mg QD as planned. If significant safety issues arise in between scheduled meetings, ad hoc meetings will be scheduled to review those data.

The decision on whether the MTD has been reached will be based on the DLT. The MTD is defined in this study as the highest single dose tested without incurring DLT. The signs and symptoms to consider for DLT include any events that in the opinion of the SRC are relevant to brensocatib exposure, including but not limited to hyperkeratosis, severe infection, and periodontal disease. The PK profile will also be considered and compared with those of other populations (healthy volunteers and patients with NCFBE) to assess whether similar levels of exposure have been achieved with the evaluated doses.

The structure of the SRC is described in [Section 10.1.8](#).

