### **6.3. Measures to Minimize Bias: Randomization and Blinding**

After meeting all inclusion criteria and none of the exclusion criteria, participants in each stratum (CFTR modulator and non-modulator) will be randomized by means of an IWRS in a 1:1:1 ratio to 1 of the first 3 dose cohorts (brensocatib 10, 25, or 40 mg); each cohort will enroll participants in a 5:1 ratio (active : placebo) for the CFTR modulator stratum. For the non-modulator stratum, approximately 6 participants will be randomized to active treatment in the first 3 dose cohorts and 1 participant will be assigned placebo. If there are no safety issues in these cohorts, a 65 mg dose cohort will be similarly randomized: 7 participants (5 participants CFTR modulator and 2 participants non-modulator stratum) in active treatment and 2 participants in placebo (1 participant each in the CFTR modulator and non-modulator strata), raising the total sample size from approximately 25 to 34 participants.

This is a single-blind study: participants are blinded to the study drug to which they are randomly assigned, as are the study center staff and the Investigator. Select Sponsor personnel comprising the SRC members and the Independent Clinical Pharmacologist are not blinded. The site will contact the IWRS prior to the start of study drug administration for each participant. The site will record the assigned study drug label number on the applicable electronic case report form (eCRF), if required.

Study personnel and participants are strongly discouraged from discussing any aspect of study treatment, with the exception of safety issues, to maintain treatment blinding and study integrity.

The IWRS will be programmed with blind-breaking instructions. In case of an emergency, the Investigator has the sole responsibility for determining whether unblinding of a participant's study drug assignment is warranted. Participant safety must always be the first consideration in making such a determination. If the Investigator decides that unblinding is warranted, the Investigator should make every effort to contact the Sponsor prior to unblinding a participant's study drug assignment unless this could delay emergency treatment of the participant. If a participant's study drug assignment is unblinded, the Sponsor must be notified within 24 hours after breaking the blind. The date and reason that the blind was broken must be recorded in the source documentation, as applicable.

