4.3. Randomization

After meeting all inclusion criteria and none of the exclusion criteria, participants in each stratum (CFTR modulator and non-modulator) will be randomized by an interactive web

response system (IWRS) in a 1:1:1 ratio to 1 of the first 3 dose cohorts (brensocatib 10, 25, or 40 mg); each cohort, will enroll participants in a 5:1 ratio (active : placebo) for the CFTR modulator stratum. For the non-modulator stratum, approximately 6 participants will be randomized to active treatment in the first 3 cohorts and 1 participant will be assigned placebo. If there are no safety issues in these cohorts, a 65 mg dose cohort will be similarly randomized: 7 participants (5 participants CFTR modulator and 2 participants non-modulator stratum) in active treatment and 2 participants in placebo (1 participant each in the CFTR modulator and non-modulator strata), raising the total sample size from approximately 25 to 34 participants.

This is a single-blind study: participants are blinded to the IP to which they are randomly assigned, as are the study center staff and the Investigator. The site will contact the IWRS prior to the start of IP administration for each participant. The site will record the assigned IP label number on the applicable eCRF, if the participant receives randomized treatment. Unblinding is only to occur in the case of participant emergencies and at the conclusion of the study.

Selected individuals not involved in the conduct of the study may have access to unblinded data as needed for safety review or other data review. These individuals comprise the SRC members and the Independent Clinical Pharmacologist (refer to CSP section 10.1.8).

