For the third ICE which is applicable for PD, Insmmed clinical team will review by participant listings of concomitant medication to judge whether antibiotics have been administered which may invalidate the use of the PD concentrations for the analysis. If this is the case, PD data after the start of such concomitant medication will be excluded from the statistical analysis.

Before DBL, the participants' data will be discussed during a Blind Data Review Meeting (BDRM). It will be decided whether ICEs occurred and up to which timepoint data for the While-On-Treatment strategy will be included in any analysis. The protocol deviation tracker will also be reviewed and discussed during the BDRM. The decisions will be documented in a Data Review Report (meeting minutes). Unblinding after DBL can only occur when the Data Review Report has been agreed upon. This will be documented by email approval. After unblinding, it will be checked if participants received treatment other than the randomized. Furthermore, it will be confirmed that the reasons to exclude participants or data records from an analysis set or analysis, respectively, are still in the same way valid as before unblinding. Any deviations between the pre-DBL and post-DBL data with an impact on decisions made during the BDRM will be documented in the final Data Review Report. If decisions made during the BDRM must be revised this will also be documented in the final Data Review Report and a rationale will be provided for the revision. The Data Review Report will only be finalized and signed after DBL.

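### The Principal Investigator sits on the unblinded Safety Review Committee although the plan says the Investigator is blinded, and nothing keeps committee members out of the later blind data review

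*Protocol*

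**What the plan says.** **Committee.** Protocol 10.1.8 lists the SRC as four functions (pipeline programs, medical monitoring, clinical pharmacology, drug safety), the "Principal Investigator for the study", and possibly outside experts. The medical monitoring member is the "Insmmed Medical Monitor for Brensocatic Clinical Development Program".

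**What it sees.** Protocol 4.1.5 has the SRC look at PK and safety data "in an unblinded manner from all cohorts to determine if brensocatib has shown an acceptable safety and PK profile" once the first three cohorts have finished. SAP 5.1 repeats this, adds PD data and fixes the time at Day 56. Both allow ad hoc meetings if a significant safety issue arises in between.

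**Who is blinded.** Protocol 6.3 says "participants are blinded to the study drug to which they are randomly assigned, as are the study center staff and the Investigator". It continues: "Select Sponsor personnel comprising the SRC members and the Independent Clinical Pharmacologist are not blinded". Protocol 1.1 and 4.2 say the same in substance. SAP 4.3 repeats the investigator blind and then says: "Selected individuals not involved in the conduct of the study may have access to unblinded data as needed for safety review". It identifies these people as the SRC members and the Independent Clinical Pharmacologist, and refers to Protocol 10.1.8.

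**The later blind review.** Under SAP 7.2, a Blind Data Review Meeting (BDRM) before database lock settles which intercurrent events occurred and how much of each participant's data is used. The sponsor's clinical team judges whether antibiotic use disqualifies PD values. General unblinding waits for the lock and an agreed Data Review Report. Under SAP 5.2, the final lock follows all four cohorts if 65 mg is run, and otherwise the first three.

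**The concern.** The plan claims a blind that its own committee structure does not deliver. A reader of the study report would take investigator assessments as blinded because three protocol sections and the SAP say so, while one investigator has been given results by arm.

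The frequency of treatment-emergent adverse events (TEAEs), compared with placebo, is a primary endpoint. The footnote to the objectives table in Protocol 3 counts clinically significant vital-sign and laboratory abnormalities in it. The Investigator makes that call (Protocol 8.1.4), so part of the count rests on judgement. The groups are small: about 7 per dose and 4 to 6 on placebo.

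The BDRM has the same weakness. Its purpose is to settle exclusions and cut-off points without knowledge of treatment. If people who have seen the first three cohorts by arm take part, that purpose is lost for those cohorts.

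**Working it through.** There is no planned figure to reproduce. The check sets the sections side by side and then counts the participants affected.

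1. **Principal Investigator against the investigator blind.** (a) The Principal Investigator is an SRC member (Protocol 10.1.8). (b) SRC members are not blinded (Protocol 1.1, 4.2, 6.3) and review data "in an unblinded manner from all cohorts" (Protocol 4.1.5). (c) The Investigator is blinded (Protocol 1.1, 4.2, 6.3; SAP 4.3). From (a) and (b) this investigator is unblinded, which contradicts (c).

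2. **Sponsor personnel.** Protocol 6.3 describes the unblinded SRC members as Sponsor staff. A Principal Investigator does not fit that description.

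3. **No role in conduct.** SAP 4.3 says people with unblinded access stand outside study conduct and points to 10.1.8, whose list includes the Principal Investigator. That is a second contradiction, independent of the first.

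4. **Medical Monitor.** Protocol 6.3 allows selected Sponsor staff to be unblinded, so this membership does not breach the investigator blind. It still does not fit SAP 4.3. The Medical Monitor has a part in decisions on interrupting study drug after an overdose (Protocol 6.7), in whether a laboratory value is still clinically significant (8.1.4) and in follow-up of possible liver injury (10.6). This assumes that the program-level monitor named in 10.1.8 is the Medical Monitor of those sections. The documents do not say.

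5. **Timing.** The scheduled review follows Day 56 of the first three cohorts (SAP 5.1). Adverse event collection ends at the Day 56 visit (Protocol 8.2.1). For those cohorts, what can still change after the review is:
   - causality, which the Investigator may revise on follow-up information (Protocol 10.3.3);
   - late or queried judgements of clinical significance;
   - serious events and events of special interest followed beyond Day 56 (Protocol 8.2.3);
   - intercurrent-event and exclusion decisions (SAP 7.2).

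6. **Share reviewed unblinded before the final BDRM, if 65 mg runs.**
   - First three cohorts: 3 × 7 active + 4 placebo = 25.
   - Fourth cohort: 7 active + 2 placebo = 9.
   - Total: 25 + 9 = 34.
   - Share: 25/34 = 73.5%, about 74%.

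   If 65 mg does not run, the order of SRC review and BDRM is not stated. The share would be 25/25 = 100% if the SRC meets first, and 0% if the BDRM does.

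7. **Safeguards.** Neither document lists BDRM attendees or the members of the clinical team, bars SRC members from either, or describes a firewall. SAP 7.2 does require decisions to be rechecked after unblinding and any revision to be justified in writing. That documents changes but does not keep the original decisions blind.

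**The case against.** **The SRC charter may already deal with this.** Protocol 10.1.8 and SAP 4.1 defer SRC conduct to it, and it may provide masked sessions or a firewall. That could protect practice but would not repair the text. If the charter masks the Principal Investigator, Protocol 6.3 is wrong to say SRC members are unblinded. If it does not, 6.3 is wrong that the Investigator is blinded.

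**The primary safety endpoint is frequency only.** This stands. SAP 3.1 summarizes counts of participant-reported events, and severity and relatedness are additional tables. Regrading an event or changing its causality does not move the primary count. Only the judgement of clinical significance can.

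**Timing removes most of the mechanism.** This largely stands. Events in the first three cohorts are recorded before the scheduled review, and the 65 mg cohort consists of new participants whose assignments the review does not reveal.

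**Consequences are limited.** This stands too. PK endpoints are assay-based, PD is exploratory, and no hypothesis is tested.

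A reader might infer more than the documents support:

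- *That unblinded meetings can happen while the first three cohorts are dosing.* The ad hoc sentence does not say the data are shown unblinded; that phrase belongs to the scheduled review.
- *That the Medical Monitor's membership breaks the investigator blind.* Protocol 6.3 permits it.
- *That the BDRM is compromised.* Attendance is not stated, so this is a missing safeguard.
- *That the size of possible bias follows from one reclassified participant.* Such a change moves a dose group by 1/7 = 14 points and placebo by 1/6 to 1/4 = 17 to 25 points. That shows how coarse the percentages are and does not estimate bias.

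**Conclusion.** The concern holds as a contradiction in the documents about the Principal Investigator's blinding status, together with an unguarded risk at the blind data review. It should be corrected.

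The contradiction rests only on the text and on reading the Principal Investigator in 10.1.8 as an Investigator in the sense of 6.3. The 74% assumes planned enrollment and that the 65 mg cohort runs. It measures how many participants' data have been seen by arm, not how many assessments are biased. The study may use more than one center (Protocol 5), so the Principal Investigator may personally assess only some of those participants. The documents do not give that share.

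They support neither a finding that adverse event recording in the first three cohorts was open to treatment knowledge as it happened, nor one that the blind review has been breached.

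**What to change.** 1. **Protocol 10.1.8 and the SRC charter:** let the Principal Investigator advise the SRC with arm labels masked. Alternatively, correct Protocol 1.1, 4.2 and 6.3 and SAP 4.3 to state that this investigator is unblinded from the SRC review onward.
2. **SAP 4.3:** reword the description of people with unblinded access so that it fits the actual members, including the Medical Monitor.
3. **SAP 7.2:** state that no one who has seen unblinded SRC data takes part in BDRM or PD-exclusion decisions. Where feasible, document those decisions for the first three cohorts before the SRC is unblinded.

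**Cost.** Items 1 and 2 are wording changes, plus a masked display if that option is taken; the investigator then advises on escalation without knowing the arms. Item 3 moves the data review of the first three cohorts earlier, adding a step before the escalation decision, and needs clinical team members who are not on the SRC.

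Taking the Medical Monitor out of the unblinded vote as well is a debatable trade-off and is not needed to resolve the contradiction. Outside experts are only a possibility under 10.1.8, so with the Principal Investigator masked it could leave three functions to decide on escalation.
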